### 3.1d Justification for exclusion criteria

- We are excluding patients with history of allergy to hydrogel dressing or skin diseases to limit the possibilities of adverse skin reactions.
- We are excluding patients with ongoing febrile illness or documented infectious disease to decrease the chances of study-related adverse effects.

## **4.0 Research Subject Entry**

### **4.1 Recruitment and Enrollment**

All pediatric patients undergoing myelosuppressive therapies for acute leukemias and other childhood cancers at Massachusetts General Hospital Cancer Center and their caregivers will be considered potential candidates for this pilot study. Recruitment information will be posted through the following online channels: Partner's Healthcare and MGH research broadcast email services (Appendix 6.1). These broadcasts are sent out to members enrolled in the broadcast at either Partners Healthcare or MGH. Additionally, the investigators will work directly with pediatric oncologists at the MGH Cancer Center to recruit their patients for this study. The hematology-oncology team, led by [name] at Massachusetts General Hospital Cancer Center will help identify potential subjects for

the study. Identified candidates could either be on hospital admission for chemotherapy or have an upcoming clinic visit for chemotherapy.

For identified candidates with upcoming hospitalization or clinic visit for chemotherapy, the research team will send out letters and study consent forms prior to the hospital visit. The letters will briefly describe the study and the study commitments. The letter will explain that a research assistant (RA) will be approaching the candidate and caregiver during their upcoming hospital visit for chemotherapy. The letter will clearly explain to the patient that if s/he does not wish to be approached by study staff, s/he should call the study line and inform the research team. If we do not hear from patients after one week of sending the recruitment letter, study staff will contact them by phone to tell them more about the study and answer any questions they may have about their participation. Additionally, study staff will leave the study informational flyers (appendix 6.0) in the pediatric oncology clinics so that oncologists will be able to introduce the study to their patients and their families. This group of patients who are directly informed about the study by their oncologists will not be sent recruitment letters.

During the clinic visit, the research assistant will provide the patient with further detail regarding the study. If the patient is interested, the RA will aim to enroll the patient during the clinic visit or a day before hospital discharge for those on hospitalization. For those patients that are already on hospital admission, the oncologist will introduce the study staff to the patient and caregiver. Before commencing study related activity, the study staff will inform patients and their caregivers about the study and give them a consent form for them to review and consider participating in the study. Study staff will return after about 30 mins – one hour to confirm their willingness or unwillingness to participate in the study.

For the interested patient-caregiver dyad, the research assistant will aim to enroll them in the study at the clinic visit or one day prior to hospital discharge by going through the consent form with the subject and caregivers to ensure adequate comprehension of study protocol. After, explaining study details and procedures, subjects and their caregivers will be given sufficient time to review the consent form and will be encouraged to ask questions. Patients who fulfill the eligibility criteria and their caregivers will be enrolled together as a dyad after the parents/legal guardians' consents to their participation. The parents/legal guardians will sign two copies of the consent form – one for the subject and the other for the study team. However, patients aged to 10 -17 years will also be required to confirm their willingness to participate in the study by signing the assent box. All enrollment procedures, including the informed consent process, will be done by research assistants. While enrollment procedures will occur during the clinic visit for chemotherapy or prior to hospital discharge, patients will not begin to use the iThermonitor until they get back home. We will also make it clear that participation in this study does not preclude participation in other research studies.

If for any reasons some patients or their caregivers needs more time to consider participating in the study, we will leave them a copy of the consent form so that they can further review the study details. No patient-caregiver dyad will be coerced into participating. We will emphasize that participation is voluntary and their non-participation will not affect their treatment. They will be asked to contact the study staff by phone if they do decide to participate. After the informed consent process, the RA will then perform all other enrollment procedures.

## **5.0 Study Design and Materials**

5.1 Study Design: This study will be implemented as a pilot study to evaluate the use feasibility of the iThermonitor as a clinical decision support tool for the continuous temperature monitoring in pediatrics patients (on myelosuppressive therapies for acute leukemia and other childhood cancers at the MGH Cancer Center) and their caregivers over a 2-week study period upon the start of device use. This will ensure that 14 days of data is collected. Apart from the enrollment and closeout procedures that will be occur in the hospital settings, all other procedures will be performed at home. The iThermonitor will only be used by the patient-caregiver dyad at home for 14 days of data collection (starting from the next day post-chemotherapy) to monitor the patient's temperature. For hospitalized patients, their 14 days will start from the first day after hospital discharge.

#### 5.2 Selection of instruments:

- An enrollment survey that will gather information regarding the dyad's demographic info and their technology use (Appendix 4.3)
- This study will use usability and satisfaction questionnaires specifically designed for this study. (Appendix 4.1)
- We will also assess caregiver anxiety with the Generalized Anxiety Disorder Questionnaire (GAD-7) (Appendix 4.2).

#### 5.3 Description of intervention:

The iThermonitor is an electronic device that continuously monitors body temperature and connects to a receiver (iPad mini) via Bluetooth to display body temperature data in real time. The iThermonitor is attached to the skin by a hydrogel dressing which can be changed as needed. It captures data even without connection to a receiver and it can establish connection to a paired receiver device (the iPad mini) within a range of three meters. The provided iPad mini will be pre-loaded with the iThermonitor app which will be used to pair the receiver with the iThermonitor device. If a caregiver prefers to use their own smart device such as an iPad, iPad mini or iPhone, study staff will install the iThermonitor app to the caregiver's device for the duration of the study. The iThermonitor monitors body temperature every four seconds and is able to store 10 days' worth of data that can be offloaded as soon as it establishes connection with a receiver. It is able to measure temperature in the range of 25-45 degrees Celsius. Users are able to set temperature limits at which alerts for which out-of-range temperature can go off. However, for this study, the range will be fixed at less than or equal to 96°F and greater than or equal to 100°F as recommended by the pediatric oncology team at MGH. This alert can be audio or visual and will be displayed on the receiver. In the event of an out-of-range temperature alert, we will encourage subjects/caregivers to confirm the alert with their usual methods of temperature monitoring or personal thermometers before notifying their care providers. In the case of a true fever, we will emphasize during the enrollment visit that subjects/caregivers should continue to monitor patients' temperature through usual care methods and also to follow usual care protocols in managing fever as recommended by their care providers. If the out-of-range temperature alert is not confirmed by their usual

temperature monitoring methods, we would encourage them to disregard the alert and log it as a false alarm.

Caregivers who have smartphones can also view their children’s temperature data on their personal smartphones (in addition to the iPad mini provided) if they wish. To be able to view temperature data on their smartphones, caregivers will have to download the iThermonitor from the Apple App and Google Play stores. The iThermonitor app is available for iPhone and Android users and there is no cost to downloading it on their phones. User manuals to guide use will be given to all subjects. (Appendices 1.4,)

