## 2.2 Primary and Secondary aims:

2.21 The primary aim of this trial is to assess the use feasibility of the iThermonitor as a clinical decision support tool in the management of patients on myelosuppressive therapies for acute leukemia and other childhood cancers. We will consider the iThermonitor as a feasible clinical decision support tool if it successfully captures body temperature data, transmit and displays the data on the iPad mini in at least 80% of the study subjects. We will also assess the ability of the device to alert the caregiver if the temperature falls outside of pre-set range which is defined for all patients as temperature less than or equal to 96 and greater than or equal to 100.

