#### 5.4 Data Collection

- The use feasibility data will be collected by a daily event monitoring log designed specifically for this study which will be recorded manually by subjects everyday throughout the study period.
- Data collected by the iThermonitor is automatically uploaded to a paired receiver within a range of five meters for cloud storage. These data will be downloaded on a weekly basis and stored in the Partners Healthcare network of computer files available to only the IRB approved study staff at the Partners Connected Health Innovation. Partners Connected Health Innovation is an established leader in the creation and implementation of effective healthcare delivery strategies supported by patient-centric technology. At PCHI, we leverage information technology – mobile phones and apps, remote monitoring tools, personal health trackers, sensors, computers and networked devices – to help providers and patients manage chronic conditions, maintain health and wellness, and improve adherence, engagement and clinical outcomes.
- We will collect information about the participant’s type of cancer, stage of disease and treatment regimens from a review of the electronic medical records.
- Enrollment, usability and satisfaction data will be collected by questionnaires designed specifically for this study.

Outcome data will be stored in computer network files that are accessible only to IRB approved study staff. Outcome data will be linked to each subject by a unique number, which will not have any identifying information. All data collected will be analyzed at the end of the study period.

A summary of data points to be assessed in this study is summarized in the table below:

Assessments	At entry	During the study	Close out (+/- 5days)
Enrollment questionnaires	X		
Temperature measurements via device	X	X	
Daily event monitoring log		X	X

Number of out-of-range temperature episodes detected		X	
Usability and satisfaction questionnaires and other closeout surveys			X
GAD-7	X		X

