**16. Did the iThermonitor alert you when your child's temperature was of out-of-range during the study period?**

- a) Yes
- b) No
- c) Prefer not to answer

*\*[If No or "Prefer not to answer", skip to question 17]*

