**17. How many times did the iThermonitor detect out-of-range temperatures? (If multiple times, please indicate number)**

- a) Once
- b) Twice
- c) 3 times
- d) Other: \_\_\_\_\_times

**18. We understand that this questionnaire may not fully capture your experiences participating in this study. Would you be interested in speaking with a research staff about your experiences in this research study?**

- a) Yes
- b) No

**Your answers are important to us. Please take a moment to check that you have answered all of the questions. Thank you for taking the time to complete this questionnaire!**

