### iThermonitor Daily Event Monitoring Log

Please indicate **Yes** or **No** for each column everyday during the study.

Day	The iThermonitor stayed on the body for most of the day		I was able to view the temperature data on the iPad mini	
	Yes	No	Yes	No
1				
2				
3				
4				
5				
6				
7				
8				
9				
10				
11				
12				
13				
14				

Caregiver Signature \_\_\_\_\_ Date \_\_\_\_\_

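### The plan promises to assess alerting and tells caregivers to log false alarms, but no visible form has a structured field for confirmation and section 6 defines no alert-performance measure

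*Combined protocol and SAP*

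**What the plan says.** After stating the 80% criterion, section 2.21 adds: "We will also assess the ability of the device to alert the caregiver if the temperature falls outside of pre-set range". Section 5.3 fixes the alert range for all children and asks caregivers to check an alert by their usual method. If that does not bear the alert out, "we would encourage them to disregard the alert and log it as a false alarm". It does not name the log it means.

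The Daily Event Monitoring Log (Appendix 5.2) has two yes/no columns for days 1 to 14. One asks whether the device stayed on for most of the day. The other reads "I was able to view the temperature data on the iPad mini".

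The assessment table in section 5.4 lists "Number of out-of-range temperature episodes detected" as a during-study item, without a source or definition. Of the device data, the same section says "These data will be downloaded on a weekly basis".

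In the close-out survey (Appendix 4.1), question 16 asks whether the device alerted the caregiver when the temperature was out of range (yes, no, or prefer not to answer). Those who answer no or decline are told "skip to question 17", which is the next question: "How many times did the iThermonitor detect out-of-range temperatures". Items 1(9) and 11c ask for opinions of the alert function, and 13d asks about problems setting alerts. Question 18 offers an interview: "Would you be interested in speaking with a research staff about your experiences in this research study".

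In section 6, 6.1a defines the primary outcome as capture, transmission and display. 6.1b(i) includes the rated usefulness of alerts, 6.7 leaves remaining outcomes to descriptive statistics, and 6.8 adopts complete-case analysis.

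**The concern.** One instruction to caregivers has no visible form on which to carry it out, and one assessment stated under the primary aim has no defined measure. The protocol itself treats the matter as important. Section 5.5 names failure to notify of a true fever, and false alerts, as the device-related risks. Section 5.67 makes alert-driven fever reporting its special concern. Section 6.1a uses daily logging for data viewing to limit recall bias, yet alert receipt is left to recall after two weeks.

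At stake are two quantities that a later study would want from this pilot: how often an out-of-range temperature led to an alert that the caregiver received, and what share of alerts the usual method did not confirm.

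**Working it through.** **The plan's own figure.** The only precision figure is +/-16 points at 80% success with 25 evaluable patients. It reproduces: 1.96 x sqrt(0.8 x 0.2 / 25) = 0.157, or 15.7 points. It concerns the capture-and-display endpoint. The documents give no target, threshold or precision for alerting, so the main check is of the text.

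**What each quantity needs, and where it could come from.**

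| Quantity | Source in the plan | Adequate? |
|---|---|---|
| Out-of-range episodes | Device data (5.4), fixed limits (5.3) | Countable once an episode is defined |
| Alert received | Close-out question 16 | One recalled yes/no per child |
| Number of alerts | Close-out question 17, if it means alerts | Recalled and ambiguously worded |
| Alert confirmed or not | No structured field | Free text (11d, 13e, 14, 15) or interview (18) only |

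**Extent of the gap in the forms.** Log rows: 25 x 14 = 350. Entries: 350 x 2 = 700, none about alerts. Five close-out items concern alerts or detections: 1(9), 11c, 13d, 16 and 17. One asks whether an alert was received, one may ask how many, and none asks about confirmation.

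**Why device data do not fill it.** Section 5.3 says the alert is displayed on the receiver. The user manual (Appendix 1.4) says the sensor goes on recording when the connection is lost, for up to 10 days. A recorded episode is therefore not the same as an alert received. Device readings also cannot show what the caregiver's own thermometer read.

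**What can be computed as written.** Each child can be classified by whether the device recorded any episode and whether the caregiver recalls an alert. A child with ten episodes and one recalled alert counts the same as a child with one of each. A recalled no, in a child with episodes, mixes alert failure, disconnection and forgetting. The unconfirmed share has no recorded numerator.

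**Burden of adding fields.** Entries per child now: 14 x 2 = 28. With one alert count per day: 28 + 14 = 42. With three confirmation entries on each of k alert days: 42 + 3k, giving 48 for k = 2, 57 for k = 5 and 84 for k = 14. The documents give no alert frequency, so k is assumed and its whole range matters.

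**If a longer log cost evaluable children (assumed).** Half-width at 80% = 1.96 x sqrt(0.16 / n): n = 25 gives 15.7 points, n = 24 gives 16.0 and n = 22 gives 16.7.

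**How wide the results would be.** As a child-level yardstick, suppose 5, 10 or 15 children have an episode and 4, 8 or 12 of their caregivers log an alert (assumed). The exact 95% intervals are 28.4-99.5%, 44.4-97.5% and 51.9-95.7%. If 3 of 10 children with an alert have an unconfirmed one (assumed), the interval is 6.7-65.2%.

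**The case against.** The strongest reply is that this is a 25-dyad descriptive pilot whose hypothesis and primary outcome omit alerting. Episodes can be counted from downloaded data against fixed limits, questions 16 and 17 ask caregivers about alerts and detections, and 6.7 provides for descriptive summaries of other outcomes. Better logging would still give wide results and would lengthen the form that feeds the primary endpoint.

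Much of this stands. A reader might infer that alerting is left with no data at all. The documents do not support that: episodes are obtainable and receipt is asked, if only by recall. Nor can one insist that question 17 counts detections and not alerts. It follows question 16 directly and may be meant as its follow-up, so the fair criticism is ambiguity and recall. A reader might also infer that confirmation data are wholly lost. Questions 11d and 15 are open text not framed around problems, and the interview could recover some of it. Finally, 5.3 does not name its log and the public copy has pages removed, so the statement can only be about the visible forms.

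What the reply does not meet is narrower. Free text and a voluntary interview give no denominator, device data cannot show confirmation, and the provision in 6.7 needs a defined variable to summarise.

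**Conclusion.** The point holds in limited form. As written, the share of alerts that were unconfirmed cannot be calculated, and alert receipt can be set against device episodes only crudely, per child, from recall. A reader might go further and suppose that the feasibility result is compromised. It is not: the success rate, its confidence interval and the 80% decision rule use only the viewing column of the log and do not depend on alerts.

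The gap is certain from the text of the visible forms. Its practical size is not, because the documents give no frequency of episodes or alerts, and every interval and alert-day count above rests on assumed numbers. The plan should be corrected, since the form change is small and daily records made at the time cannot be replaced by later recall. The gain would be a descriptive estimate and no more.

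**What to change.** - **Appendix 5.2:** add a section apart from the two primary-endpoint columns, with the daily number of alerts received (0 if none) and the number not confirmed by the usual method, with not checked as an option.
- **Section 6.8:** state that blank alert entries do not make the primary columns incomplete.
- **Sections 6.1 and 6.7, receipt:** define an out-of-range episode in advance. Among child-days with a device-recorded episode, report the share with a logged alert. Report disconnected periods separately where the data allow, and note that a missing entry cannot be told from a missed alert.
- **Sections 6.1 and 6.7, confirmation:** report the number of alerts and the share unconfirmed, per child and pooled. Give no simple binomial interval for the pooled share, because alerts cluster within a child.
- **Appendix 4.1:** reword question 17 to say whether it counts alerts or detections, and make the question 16 skip match that meaning. As printed it skips nothing.

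The cost is a revised log, a few lines in the analysis plan and two form edits. Each child's log grows from 28 entries to 42 plus the confirmation entries on alert days. With one such entry per alert day the ceiling is 42 + 14 = 56, and with three it is 84. Keeping the alert section separate and outside the complete-case rule limits the risk to the primary endpoint. Under-logging and wide estimates remain possible. Alert limits and care instructions do not change.

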#### 5.4 Data Collection

- The use feasibility data will be collected by a daily event monitoring log designed specifically for this study which will be recorded manually by subjects everyday throughout the study period.
- Data collected by the iThermonitor is automatically uploaded to a paired receiver within a range of five meters for cloud storage. These data will be downloaded on a weekly basis and stored in the Partners Healthcare network of computer files available to only the IRB approved study staff at the Partners Connected Health Innovation. Partners Connected Health Innovation is an established leader in the creation and implementation of effective healthcare delivery strategies supported by patient-centric technology. At PCHI, we leverage information technology – mobile phones and apps, remote monitoring tools, personal health trackers, sensors, computers and networked devices – to help providers and patients manage chronic conditions, maintain health and wellness, and improve adherence, engagement and clinical outcomes.
- We will collect information about the participant’s type of cancer, stage of disease and treatment regimens from a review of the electronic medical records.
- Enrollment, usability and satisfaction data will be collected by questionnaires designed specifically for this study.

Outcome data will be stored in computer network files that are accessible only to IRB approved study staff. Outcome data will be linked to each subject by a unique number, which will not have any identifying information. All data collected will be analyzed at the end of the study period.

A summary of data points to be assessed in this study is summarized in the table below:

Assessments	At entry	During the study	Close out (+/- 5days)
Enrollment questionnaires	X		
Temperature measurements via device	X	X	
Daily event monitoring log		X	X

Number of out-of-range temperature episodes detected		X	
Usability and satisfaction questionnaires and other closeout surveys			X
GAD-7	X		X

